Aim: The aims of this study are to determine the feasibility and acceptability of the simplified 10-step Tai-chi programme for PWD, and to explore the preliminary effects of this intervention on the motor performance of PWD.

Design: A single-blinded cluster RCT will be used to compare the experimental and the control groups. An independent, trained research assistant (RA-assessor) who is blinded to the group assignment will perform the outcome assessments and data entries. A descriptive, qualitative design with focus groups or individual interviews will be used to evaluate the process of implementing the intervention from the perspectives of the participants, their caregivers, and the Tai-chi instructor.

Setting and Sampling: Four community health centres which provide services to PWD will be invited by a convenience sampling method to participate in the study. We will only recruit those community health centres that are funded by the Hong Kong (HK) government and that are under the supervision of Social Welfare Department, which meet a specific set of standardized regulations and criteria on practices, and which provide similar sets of care services for community-dwelling older people. The study's target population is community-dwelling older people with mild to moderate dementia.

The inclusion criteria for participants are: 1) community-dwelling older people of either gender; 2) who are able to communicate in Cantonese to ensure that they understand our instructions during the training, 3) who are able to walk independently with no walking aid or no more than a single point stick for at least 10 minutes so as to ensure their mobility is good enough to allow them

to take part in the Tai-chi training. 4) They must also have received a formal diagnosis of any form of dementia. Their level of cognitive impairment will be assessed using an Abbreviated Mental Test (AMT)^{28, 29} with a score ranging between 5 and 8 to indicate mild to moderate cognitive impairment. 5) Finally, they must identify a caregiver who is willing to work as an exercise partner and facilitator for their practice of Tai-chi.

Sample size: Thirty participants will be recruited for each group. A small sample of 30 per group would be sufficient to test the feasibility of a pilot study³⁰. Twenty participants from the experimental group will be randomly selected to join the focus groups after completing the entire programme.

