Sample recruitment procedures: The centres will be randomized into the control or the Tai-chi groups by using computer-generated random numbers for each of the four centres generated by an independent statistician. We will publicize/promote this study by displaying posters in the centres and asking the centre-in-charges to encourage and refer the eligible subjects to participate. A leaflet containing information about the study and an invitation letter with a reply slip for the participants to indicate their interest in participating in the study will also be mailed to all potential subjects to invite them to participate in this study. A convenience sampling method will be used to recruit participants in the community health centres.

The Interventions

The experimental condition: A 16-week 10-step simplified Tai-chi group training programme will be arranged for the Tai-chi group. During the intervention period, the participants in the Tai-chi group will receive two 1-hour centre-based Tai-chi group training sessions every week.

The participants will be required to pair up with their caregiver to take part in the training sessions together. They will be encouraged to practice the Tai-chi exercises at home for 30 minutes for at least three times per week. Adding up all of the group sessions and the time spent practising at home, each participant should have undergone at least 56 hours of Tai-chi practice during the intervention period. A high dose of 50 hours of exercise practice has been shown to be more effective in reducing fall rates than exercise interventions that require less than 50 hours of practice³¹. A maximum of 7-8 pairs of participants and their caregivers will be supervised by a qualified Tai-chi instructor during each training session. To encourage the participants to practise the Tai-chi exercises at home, a compact disc and a pamphlet describing the 10-step Tai-chi programme will be distributed.

The control condition: As no active fall prevention treatments have been employed among local older people with dementia, the control group will only take part in group recreational activities organized by the district centres. The number and timing of the activities will be similar to those organized in the Tai-chi training session for the experimental group. The participants in the control group will be also instructed to continue their usual lifestyles and levels of physical activity.

Instruments and Measures

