- Dynamic single leg standing balance will be assessed by the Step Test (ST) test³⁸. Participants will stand with their feet parallel and apart for about 10 cm. A block / step with 7.5 cm height will be placed 5 cm in front of the participants. They will be instructed to place the whole foot onto the block, then return it fully back down to the floor repeatedly as fast as possible for 15 seconds. Each leg will be tested separately, and performance on the left or right side with the least number of steps will be the result.

The number of falls will be also recorded by the caregivers and the participants in a monthly falls calendar, in which they will note down any fall accidents that have happened to the participant during the 16-week study period. Monthly phone calls will be made by an RA-observer to remind the participants to return the calendar as well as to verify the records. A fall will be defined as “an unexpected event in which participants come to rest on the floor or lower level⁴¹.” This will be used to guide the participants (caregivers) in recording their fall accidents. The severity of the injuries will also be recorded.

Procedures (randomization, allocation concealment, blinding)

After ethical approval has been obtained, all potential participants will be screened for their eligibility to participate in the study. The participants and their caregivers will then be interviewed to obtain their proxy informed consent, socio-demographic data, and baseline assessment. After that, the four community centres will be randomized to the control or the experimental groups. The participants from each centre will be placed into their centre’s corresponding group to avoid ‘contaminating’ other participants. The changes in the above mentioned preliminary outcome scores from the baseline to interim assessment at Week 8 (T1:Mid-term of intervention) and intervention effects at immediate (T2) after completion of the 16-week interventions will be compared between the groups by the RA-observer.

Twenty participants from the Tai-chi group will be randomly selected to join the focus groups within two weeks after completing the entire programme. Each focus group will contain between 5 and 10 people. The Tai-chi instructor will also be interviewed individually. All interviews will be conducted by the PI in the community health centres to collect the opinions on the design of the intervention. (Appendix II: Timeline of the study)

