Official Title: The Effects of Simplified 10-step Tai-chi Programme
on the Motor Performance and Fall Prevention of Community-
dwelling Older People With Dementia: a Pilot Cluster Randomized
Control Trial

Date of the document: 16 May 2016

**The effects of a simplified 10-step Tai-chi programme on the motor performance and fall prevention of community-dwelling older people with dementia (PWD):
A pilot cluster RCT study**

Statistical Analysis

SPSS will be used for data analysis. Descriptive statistics will be generated for the demographic data. Normality assumptions for the variables will be checked. The paired t-test or Wilcoxon's signed rank test will be used to examine any significant difference in outcome measurements in the experimental group before and after the implementation of the combined intervention. Student's T-test or the Mann-Whitney U test will be used to examine any significant differences between the control and experimental groups in terms of the outcome variables. For categorical and dichotomous outcome variables, a χ^2 test will be used to identify any significant differences between the groups. A p-value < 0.05 will be considered statistically significant. Mixed effect modelling (MEM) will be further used to measure changes in the outcome measures after intervention with respect to its baseline, and to see the effectiveness of the intervention. Multiple imputations will be adopted to manage missing data.

All interviews will be transcribed and analyzed by content analysis so as to understand participants', caregivers' and the Tai-chi instructor's opinions about the intervention. Coding will occur independently by two members of the research team. Differences in coding between the independent coders will be resolved through discussion between the coders

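### The stated between-group test of the motor outcomes ignores centre, the randomised unit, and no main analysis is named: make a baseline-adjusted centre-level comparison on 2 df the main one

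*SAP*

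**What the plan says.** Centres are the randomised unit. The Protocol (Sample recruitment procedures) states: "The centres will be randomized into the control or the Tai-chi groups by using computer-generated random numbers for each of the four centres". Its Procedures section, after describing consent and baseline assessment, repeats: "After that, the four community centres will be randomized to the control or the experimental groups".

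The SAP and the Protocol's Statistical Analysis section describe the same quantitative analyses:

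- A paired t-test or Wilcoxon test of "any significant difference in outcome measurements in the experimental group before and after the implementation of the combined intervention". This looks inside one arm only, so it cannot estimate a difference between arms.
- A t-test or Mann-Whitney test to "examine any significant differences between the control and experimental groups in terms of the outcome variables". No centre term and no baseline covariate is mentioned, and significance is judged at 0.05.
- A mixed model: "Mixed effect modelling (MEM) will be further used to measure changes in the outcome measures after intervention with respect to its baseline". No fixed effects, random effects or df method are listed.

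Neither document says which of these gives the main between-group result.

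On scale, the Protocol (Procedures) compares "The changes in the above mentioned preliminary outcome scores from the baseline to interim assessment at Week 8", but for the end of treatment says only that "intervention effects at immediate (T2) after completion of the 16-week interventions will be compared between the groups". The simple test is not tied to a scale in either document.

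The motor tests serve a stated aim (Protocol, Aim): "to explore the preliminary effects of this intervention on the motor performance of PWD".

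**The concern.** People from one centre share staff, activities and catchment, and all of them receive the same allocation. If centres differ in motor outcome for reasons other than Tai-chi, a test that counts 60 independent people treats those differences as treatment effect, and its standard error is too small. The mixed model could deal with this, but its description fits a model with a participant effect alone just as well as one with a centre effect.

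The stake is the exploratory motor result. Low power is acceptable in a pilot; an interval that is too narrow is not. The Protocol looks ahead to a main study, and an understated standard error could mislead its planning.

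**Working it through.** **The plan's own figure.** The only one is 30 per group (Protocol, Sample size). It rests on a pilot rule of thumb with no effect size, SD, power or ICC, so there is no calculation to reproduce.

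**Inputs.** From the documents: four centres, 30 per group, significance at 0.05. Assumed: two-sided test, two centres of 15 per arm, ICC 0.01 to 0.10, baseline-to-follow-up correlation r of 0.5 to 0.8, complete normal data with total variance 1.

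**Step 1: type I error of the stated test.** The design effect is DE = 1 + (15 - 1) x ICC, and the actual error is about 2 x [1 - Phi(1.96 / sqrt(DE))]. The simulated columns are for the t-test.

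| ICC | DE | Formula | Simulated, single time point | Simulated, change score (r = 0.7) |
|---|---|---|---|---|
| 0.01 | 1.14 | 6.6% | 6.4% | 6.7% |
| 0.02 | 1.28 | 8.3% | 8.5% | 8.5% |
| 0.05 | 1.70 | 13.3% | 13.7% | 13.6% |
| 0.10 | 2.40 | 20.6% | 21.3% | 21.2% |

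Mann-Whitney is similar (about 13% at ICC 0.05 and 20% at 0.10). A baseline covariate without a centre term gives 13-14% and 20-21%.

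**Step 2: how far this depends on stability of centres.** Let c be the correlation over time of the centre effects. The ICC of the change score is (1 - c) x ICC / [(1 - c) x ICC + (1 - r)(1 - ICC)]. If c = r, this equals the ICC, which is the case in the table. With ICC 0.05, r = 0.7 and c = 0.90 it is 0.005 / (0.005 + 0.285) = 0.017, so DE = 1.24 and the error is about 8%. Simulation gives 8%, 7% and 5% for c = 0.90, 0.95 and 1.

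**Step 3: centre-level analysis.** For each centre, take the mean of the week-16 value minus the pooled within-centre slope times baseline, and compare arms on 4 - 2 = 2 df. Simulated type I error is about 5% in every null setting tried.

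**Step 4: the mixed model.** With a random centre effect, no baseline covariate and one time point, Wald z gives 8.8% at ICC 0.05 and 12.0% at 0.10; 58 df gives 8.3% and 11.4%. With baseline, two time points and Satterthwaite df, the error is 6.1-6.6% and 7.8-8.3%. The centre variance is estimated as zero in about 43% and 32% of trials. Fixed centre effects are no alternative: four centre dummies plus arm make five columns of rank 4.

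**Step 5: baseline adjustment.** Against change scores, with c = r, the SE falls by 1 - sqrt((1 + r)/2) = 13%, 8% and 5% at r = 0.5, 0.7 and 0.8. With c = 1 and ICC 0.10 this reverses: the SD of the estimate is 0.263, 0.200 and 0.162 adjusted, against 0.246, 0.190 and 0.155 for change.

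**Step 6: price of the centre-level analysis at ICC 0.05, r = 0.7.**

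- Centre level: true SE = sqrt(2 x 0.51 x 1.70 / 30) = 0.240. The median estimated SE on 2 df is sqrt(ln 2) = 0.83 of that, so the median half-width is about 4.303 x 0.83 x 0.240 = 0.86 SD (simulated 0.87).
- Change t-test: the nominal SE is sqrt(2 x 0.60 / 30) = 0.200, giving 2.002 x 0.200 = 0.40 SD (simulated 0.39). Its true SE is 0.200 x sqrt(1.70) = 0.261.
- Simulated power for an assumed 0.5 SD effect is about 23% at centre level and 66% for the change t-test.

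**The case against.** The strongest reply is that this is a feasibility pilot with exploratory motor outcomes, that a mixed model is planned, and that the Protocol restricts recruitment to centres under common regulations with similar services, so the ICC may be small. Much of this stands. At ICC 0.01 the inflation is slight, and four centres cannot support a confirmatory test by any method: an exact permutation over a 2:2 split has six allocations, so its smallest two-sided p-value is 2/6 = 0.33. What does not stand is the inference that an exploratory status excuses a standard error that ignores the unit of randomisation.

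Four stronger readings are tempting, and the documents do not support them.

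- *That every planned analysis omits centre.* The mixed model's terms are unstated; centre is neither shown to be in it nor shown to be left out.
- *That the plan ignores baseline.* The mixed model is described relative to baseline and the Protocol compares changes at Week 8. Only the covariate and the T2 scale are unsettled, and change is the better supported reading.
- *That both raw and change values would be tested and either one reported.* No passage proposes this.
- *That using baseline can never ease the clustering problem.* Step 2 shows that change scores remove fully stable centre differences. The documents give no information on that stability.

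It is also tempting to make the mixed model the main analysis and fall back on the centre-level result only when the centre variance is estimated as zero. This should not be done. Those are the trials in which the centre means happened to lie close together, and within them the centre-level test still errs about 12% of the time at ICC 0.05 and 16% at 0.10. The switch is also undefined when imputed data sets disagree. A plain centre-level analysis holds about 5% overall, with nearly the same power (23% against 26% for the switch).

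**Conclusion.** The concern holds for clustering and for the missing main analysis. The stated test does not analyse by the randomised unit, and the documents do not show that the mixed model does. The size of the error rests on the assumed ICC, the assumed 2:2 split into centres of 15, and centre effects that correlate over time as individuals do. Across the ICC range of 0.01 to 0.10 it runs from a small excess over 5% to about four times the nominal level. The baseline part is secondary: a gain of about 5-13% of the SE against change scores, which can reverse. The plan should be amended, but the finding concerns an exploratory aim and does not touch feasibility. Falls and categorical outcomes were not examined here.

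**What to change.** In the SAP and the Protocol's Statistical Analysis section:

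1. Name one main between-group analysis of each motor test at week 16 (T2): the baseline-adjusted centre-level comparison in step 3, with a t reference on number of centres minus 2 (2 df).
2. Report the estimate and 95% interval as a preliminary effect. Combine results over the planned imputed data sets by a stated rule that keeps the 2-df reference.
3. Keep the mixed model as supportive, with baseline, group, time and group-by-time as fixed effects, participant and centre as random effects, and a stated small-sample df method (Kenward-Roger or Satterthwaite). Do not switch between analyses on whether the centre variance is estimated as zero.
4. Label the t/Mann-Whitney and within-arm paired tests descriptive.

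In the Protocol's Procedures section, state the T2 scale so that it matches the SAP.

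The change needs no new data. Its cost is precision: in the setting of step 6, intervals about 2.2 times as wide (0.87 / 0.39) and power of about 23% instead of 66%. That 66% comes from a test with about 13% type I error, so it is not a fair benchmark.

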- Exercise adherence will be assessed weekly based on the caregiver report in an exercise diary on the days and duration that the participant practises Tai-chi. This diary will be collected every week during the 16-week training period. Weekly phone calls will be made by an RA to remind the participants to return the diary as well as to verify the records. Attendance in the Tai-chi training sessions will also be recorded as evidence of adherence to the training programme.
- The occurrence of adverse events will be recorded which include the date, the time, the unanticipated bodily response and symptoms (e.g. fall, fatigue, dizziness), and the immediate treatment provided.
- Collection of feedback from all stakeholders – Feedback from participants and their caregivers will be collected by focus group within two weeks after completing the entire Tai-chi programme. An individual interview will be conducted to collect opinions from the Tai-chi master. The interview guides for different stakeholders will be set up. A panel of experts will be invited to review the interview guide to evaluate the appropriate of the questions. The interview will be audiotape recorded and transcribed verbatim.

Preliminary outcomes assessment: motor performance

- Mobility will be assessed by the Timed-up-and-Go (TUG) test^{34,35}. The time taken by participants to execute the tasks – stand up from a standard chair, walk three meters, turn around, walk back to the chair and sit down will be recorded in seconds.
- Functional limb muscle strength will be assessed the Timed-Chair-Stand (TCS) test³⁶. Each participant will be asked to sit at the front edge of a standard chair with their arms crossed, and instructed to stand up fully and sit down five times as quickly as possible. Time to complete this task will be recorded.
- Dynamic bilateral stance balance will be assessed by the Functional Reach (RF) test³⁷. Participants will stand beside a wall with their feet apart for about 10 cm and raise their dominant arm to 90 degrees. They will then be instructed to lean forward as far as possible with the hand remaining at shoulder level. The FR score will be the additional reach of the raised hand from the starting position in cm.

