All workshops and Tai-chi sessions must follow the protocols and will be run by the same RA/Tai-chi instructor to ensure intervention consistency. Intervention fidelity checking will be conducted in the training period and then monthly to bimonthly during the intervention period based on the workshop/ Tai-chi checklists. Achieving a fidelity rate of >90% will be considered acceptable, based on the recommendations of the NIH Behaviour Change Consortium⁴². This is to ensure that all of the interventions are executed by the Tai-chi instructor or the RA as intended. Monthly to bi-monthly quality-control meetings with all research personnel (the Tai-chi instructor and the RA) will be arranged to evaluate their instruction / facilitation skills in this study.

Statistical Analysis

SPSS will be used for data analysis. Descriptive statistics will be generated for the demographic data. Normality assumptions for the variables will be checked. The paired t-test or Wilcoxon's signed rank test will be used to examine any significant difference in outcome measurements in the experimental group before and after the implementation of the combined intervention. Student's T-test or the Mann-Whitney U test will be used to examine any significant differences between the control and experimental groups in terms of the outcome variables. For categorical and dichotomous outcome variables, a χ^2 test will be used to identify any significant differences between the groups. A p-value < 0.05 will be considered statistically significant. Mixed effect modelling (MEM) will be further used to measure changes in the outcome measures after intervention with respect to its baseline, and to see the effectiveness of the intervention. Multiple imputations will be adopted to manage missing data.

All interviews will be transcribed and analyzed by content analysis so as to understand participants', caregivers' and the Tai-chi instructor's opinions about the intervention. ???Coding will occur independently by two members of the research team. Differences in coding between the independent coders will be resolved through discussion between the coders.

Ethical Consideration

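### One blanket p < 0.05 rule covers four motor tests at two follow-ups, with no main test, main time point or multiplicity limit, in a pilot that only aims to explore motor effects

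*SAP*

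**What the plan says.** The SAP and the protocol's Statistical Analysis section carry the same rule: "A p-value < 0.05 will be considered statistically significant". It is attached to no particular outcome or time point. Three kinds of test fall under it:

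- paired tests within the Tai-chi arm;
- between-arm tests ("Student's T-test or the Mann-Whitney U test will be used to examine any significant differences between the control and experimental groups");
- chi-squared tests for categorical outcomes.

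A mixed model follows, one purpose of which is given as "and to see the effectiveness of the intervention".

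The protocol, under Preliminary outcomes assessment: motor performance, gives the outcomes: "Mobility will be assessed by the Timed-up-and-Go (TUG) test"; "Functional limb muscle strength will be assessed the Timed-Chair-Stand (TCS) test"; "Dynamic bilateral stance balance will be assessed by the Functional Reach (RF) test"; and the Step Test for single-leg balance. Under Procedures, the arms are to be compared on changes "from the baseline to interim assessment at Week 8 (T1:Mid-term of intervention) and intervention effects at immediate (T2"), the second assessment coming at the end of the 16-week programme.

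The Aim puts feasibility and acceptability first. On motor performance it intends only "to explore the preliminary effects of this intervention on the motor performance of PWD". Neither document names a main motor test or a main time point, gives a hierarchy or adjustment, or limits how a single small p-value may be reported.

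**The concern.** The aim is exploratory, but the analysis section is worded as for a confirmatory trial. Calling the aim exploratory does not restrict what the 0.05 rule allows. As written, any one of the motor comparisons, at whichever follow-up produced it, may be labelled statistically significant. A reader who sees that label will assume a 5% chance of a false finding. Across the set of comparisons the chance is several times larger.

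The protocol looks ahead to a main study when it describes the feasibility assessment. A chance difference in one test at one visit could therefore influence which outcome that study adopts, or what effect size it plans for.

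**Working it through.** There is no stated error calculation to reproduce. The 0.05 threshold is the only error-rate figure in either document, and the 30 per group rests on a citation.

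**Inputs from the documents**
- Threshold per test: 0.05 (SAP; protocol, Statistical Analysis).
- Motor tests: 4 (protocol, Preliminary outcomes assessment).
- Follow-ups: 2, T1 at Week 8 and T2 after Week 16 (protocol, Procedures).
- Between-arm comparisons: 4 × 2 = 8.

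**Assumptions**
- Tests are two-sided. The documents do not say, but the wording gives no direction.
- Each single test keeps a true 5% error.
- Correlations between test statistics are not given in the documents. The ranges used are 0.3–0.8 between motor tests and 0.5–0.9 between T1 and T2.

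**Step 1: independent comparisons, either direction**
- All eight: 1 − 0.95^8 = 1 − 0.663 = 33.7%.
- The four tests at T2 only: 1 − 0.95^4 = 1 − 0.815 = 18.5%.

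**Step 2: independent comparisons, results favouring Tai-chi only**
- Each two-sided test has 2.5% in that direction, so 1 − 0.975^8 = 1 − 0.817 = 18.3%.

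**Step 3: correlated comparisons**
Eight normal statistics (4 tests × 2 times) were simulated under no effect with 300,000 draws per setting. A comparison counts as significant when |z| > 1.96.

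| Correlation between tests / between times | At least one, either direction | At least one favouring Tai-chi |
|---|---|---|
| 0.3 / 0.5 | 29.8% | 15.2% |
| 0.5 / 0.7 | 24.9% | 12.4% |
| 0.7 / 0.7 | 20.8% | 10.4% |
| 0.7 / 0.9 | 17.8% | 8.8% |
| 0.8 / 0.9 | 15.6% | 7.8% |

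For the four T2 comparisons alone, the either-direction rate is 15.6% at a between-test correlation of 0.5 and 13.0% at 0.7.

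**Step 4: what the count leaves out**
The eight do not include the within-arm paired tests, the mixed-model tests or falls. Each adds further chances of a small p-value.

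**Step 5: the 5% assumption**
Four centres are randomised. If an unadjusted t-test is used with an assumed two centres of 15 per arm, simulation gives a per-test error of about 6.6% at an assumed intra-cluster correlation of 0.01 and 13.5% at 0.05. The figures in Steps 1–3 therefore show the effect of multiplicity alone and come before any effect of clustering.

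**The case against.** The strongest reply is that this is a pilot and need not control a family-wise error rate. The title says pilot, feasibility and acceptability come first, and the motor measures are repeatedly called preliminary. That stands: no Bonferroni-type correction is asked for here. It does not answer the mismatch between an exploratory aim and an unconditional significance label.

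A second reply is that the protocol already leans towards T2, since it calls Week 8 interim and speaks of intervention effects at T2. That is fair, but it falls short of naming T2 as the main time point. With T2 alone, four tests still give 13.0–18.5% over independence and the assumed correlations of 0.5 and 0.7.

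Three stronger readings are tempting, and the documents do not support them.

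- A reader might infer that a spurious Tai-chi benefit appears in a fifth to a third of null trials. Rates of that size count differences in either direction. A chance result favouring Tai-chi is about half as frequent. The lower end also depends on correlations that the documents do not give.
- A reader might infer that the SAP lets one small p-value out of eight stand as proof of effectiveness. The phrase "and to see the effectiveness of the intervention" belongs to the mixed-model sentence, not to the t-tests counted here.
- A reader might take the eight comparisons as listed in the SAP. They come from reading its general rule together with the protocol's outcome and procedure sections. The inference is reasonable, but it is an inference.

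**Conclusion.** The point holds. One unconditional 0.05 rule covers four motor tests at two follow-ups, with no main test, main time point or multiplicity limit, although the aim is exploratory.

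With no true effect, the chance of at least one significant group difference in either direction is up to about 34% if the eight comparisons are independent, and about 16–30% under the assumed correlations. The chance of one favouring Tai-chi is about 8–18%, against 2.5% for a single two-sided test. These are illustrations of multiplicity, conditional on valid single tests. They are not predictions of this trial's actual error rate.

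The consequence is a licence to over-report. It does not undermine the feasibility aims, but it should be corrected because the correction is cheap.

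**What to change.** Make these changes in both the SAP and the protocol's Statistical Analysis section.

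1. State that the motor and fall outcomes are exploratory.
2. State that the between-arm difference for TUG, TCS, Functional Reach and Step Test is reported with a 95% confidence interval, with T2 as the main time point and T1 as supportive. T2 is the natural choice because it follows the full programme. The planned minimum practice is 16 × (2 × 1 h + 3 × 0.5 h) = 56 h by T2 and 8 × 3.5 h = 28 h by T1. Home practice is only encouraged, so these are planned hours, not delivered ones.
3. Delete the p < 0.05 sentence.
4. Reword all three testing sentences (within-arm paired, between-arm, chi-squared) so that they describe estimates instead of a search for significant differences. Add that within-arm change is not used as evidence of effect. If these sentences were left alone, they would contradict items 1–3.
5. Replace "and to see the effectiveness of the intervention" with *to estimate the preliminary effect*.

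The coverage of the intervals will still depend on how the four centres are handled, which these edits do not settle.

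The cost is the loss of the significant label and the editing of several sentences in each document. No extra participants, visits or data are needed.
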